14.3.1 Study Populations

Three populations will be used in the analyses of the data:

1. The intent-to-treat (ITT) population will consist of all randomized subjects; this population will be used for efficacy analysis, including primary endpoint (progression-free survival). Subjects will be analyzed as randomized.

2. The per protocol (PP) population is defined as all randomized subjects who received at least two cycles (8 weeks) of protocol treatment (unless discontinued due to death or disease progression), have no major protocol deviations that will confound the effects of treatment, and meet all eligibility criteria. Major protocol deviations include but are not limited to failure to satisfy eligibility criteria and taking prohibited medications during the treatment phase of the study. Subjects will be analyzed as treated.
3. The safety population (SAF) will include all subjects who received at least one dose of either study drug. Subjects will be analyzed as treated.

14.3.2 Subject Accountability, Demographics, and Baseline Characteristics

All subjects enrolled (signed informed consent) in the study will be included in the summary of subject accountability by treatment arm and region. The frequency and percentages of subjects who were enrolled in the study, discontinued from treatment before having documented disease progression, or discontinued from the study due to documented disease progression will be summarized for the ITT population.

Descriptive statistics of subject demographics (age, gender, ethnicity, and race) and baseline characteristics will be summarized and presented by treatment arm.

14.3.3 Protocol Deviations

A subject will be classified as having a protocol deviation if one incurs an event belonging to any one of the following categories: 1) violation of the inclusion/exclusion criteria; 2) taking prohibited medications or treatments; 3) treatment misallocation; 4) violation of discontinuation criteria; 5) error in procedures and tests; and 6) missed visits. Other deviation categories may be identified as appropriate.

14.3.4 Efficacy

The primary efficacy endpoint (PFS) and secondary efficacy endpoints (OS, ORR, and DoR) analyses will be carried out using the ITT population. The primary efficacy endpoint of PFS also will be analyzed using the PP population.

Analysis of the Primary Endpoint

The primary analysis is to compare the PFS of subjects dosed with tivozanib with those subjects dosed with sorafenib. The null hypothesis is that the median tivozanib PFS is equal to that of sorafenib and the alternative hypothesis is that the two PFS medians are not equal. The IRR will be the primary data source for the PFS analysis.

The primary analysis will be carried out by using a stratified Log-Rank test, in which the stratification factors are IMDC risk category (favorable; intermediate; poor) and prior therapy (two prior VEGFR TKIs; a prior checkpoint inhibitor [PD-1 or PD1 L inhibitor] plus a prior VEGFR TKI; a prior VEGFR TKI plus any other systemic agent), and using a two-sided 5% significance level. The distribution of the PFS will be estimated using the Kaplan-Meier method. The median event time and 2-sided 95% confidence interval for the median will be also provided.

Interim Analysis

An interim analysis will be performed after 128 PFS events have been observed. The interim analysis will look into the study's futility using PFS as the efficacy evaluation endpoint. This will utilize a Lan-DeMets error spending-type function with an O'Brien-Fleming stopping boundary with an estimated two-sided beta (Type II error) of 1.2 % spent during this interim look.

The interim analysis will be performed by an independent statistician. The independent statistician will evaluate and interpret the results of the interim analysis and will provide corresponding recommendation whether to stop the study for futility or for the study to continue until end of study condition has been met.

Final analysis performed on PFS will be based on 255 events. This could be performed ≥ 6 months after the last subject is accrued. PFS interim and final analyses will be carried out by using a stratified Log-Rank test with IMDC risk category and prior therapy as stratification factors.

Handling of Missing Data

For the purpose of PFS analyses, the following steps will be considered in case of missing data:

- a) Subjects with missing imaging at baseline will be considered non-evaluable for PFS estimation and will be excluded from the PFS analyses
- b) Subjects who have no tumor assessment after randomization will have PFS censored at the date of randomization, unless they died before the second scheduled tumor assessment.

Further details and other cases will be described in the statistical analysis plan (SAP).

Analysis of Secondary Endpoints

The secondary endpoints (OS, ORR, and DoR) will be analyzed using the investigator and independent radiological review assessments. The degree of agreement between the investigator and the independent assessment of responses will also be summarized and presented in a table.

The first secondary analysis will compare the OS between the 2 treatment arms by using stratified Log-rank test and the stratification factors included in the primary analysis. An interim OS analysis will be carried out at the time of the Final PFS analysis.

Duration of response (DoR) will be analyzed using the same method as for the progression-free survival.

The proportion of subjects achieving confirmed ORR (complete response [CR]+partial response [PR]) will be summarized and presented by treatment arms and cycle and will be compared between the two treatment arms using Cochran-Mantel-Haenszel (CMH) test with the same stratification factors used for the PFS analysis.

Exploratory Analyses

In order to evaluate if the timing of post-baseline radiological scan influenced the primary outcome, the time from randomization to post-radiological scan will be calculated and an exploratory analyses will be conducted. Means and standard deviation of radiological scan time will be presented by treatment arms and cycle time. Log-rank test will be used to test if cumulative percentages (survival curves) are equal (median time to each cycle from randomization) by treatment arms.

Subgroup Analyses

PFS subgroup analyses by gender, race, and age (< 65 years and \geq 65 years) will be carried out using separate unadjusted Log-rank test for the ITT population.

Definition of Efficacy Endpoints

Progression-Free Survival (PFS) is defined as the time from randomization to first documentation of objective tumor progression (progressive disease [PD], radiological) according to RECIST (Version 1.1) or death due to any reasons whichever comes first. PFS data will be censored on the day following the date of last tumor assessment documenting absence of PD for subjects who do not have objective tumor progression and are still on study at the time of the analysis, are given anti-tumor treatment other than the study treatment, or are moved from treatment follow-up prior to documentation of objective tumor progression. Subjects having no tumor assessments after randomization who are not known to have died will have PFS censored on the date of randomization.

Overall survival (OS) is defined as the time from the date of randomization to date of death due to any cause. In the absence of confirmation of death, survival time will be censored at the last date the subject is known to be alive. Subjects lacking data beyond randomization will have their survival times censored on the date of randomization.

Overall response rate (ORR) is defined as the proportion of subjects with confirmed CR or confirmed PR according to RECIST (Version 1.1), relative to the total population of randomized subjects. Confirmed responses are those that persist on repeat imaging study at least 4 weeks after the initial documentation of response.

Duration of response (DoR) is defined as the time from the first documentation of objective tumor response to the first documentation of objective tumor progression or to death due to any cause. DoR data will be censored on the day following the date of the last tumor assessment documenting absence of PD for subjects who do not have tumor progression and are still on the study at the time of an analysis, are given antitumor treatment other than the study treatment, are removed from the study follow-up prior to documentation of objective tumor progression, died of non-cancer related cause, including death due to unknown cause in the absence of documented disease progression. **DoR will only be calculated for the subgroup of subjects with an objective tumor response (PR or CR).**

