Data will be summarized using descriptive statistics (number of subjects, mean, median, standard deviation, minimum, and maximum) for continuous variables and using frequency and percentages for discrete variables.

The primary analysis will compare the distribution of the PFS between the two treatment arms by using the stratified Log-rank test, in which the stratification factors are IMDC risk category (favorable; intermediate; poor) and prior therapy (two prior VEGF TKIs; a prior checkpoint inhibitor [PD-1 or PD1-L inhibitor] plus a prior VEGFR TKI; a prior VEGFR TKI plus any other systemic agent). PFS will be based on the CT or MRI scan assessed by the IRR. PFS graphs will be presented by treatment arm.

The first secondary analysis will compare OS between the 2 treatment arms by using the stratified Log-rank test, the stratification factors included in the primary analysis, and two-sided 0.8% significance level (utilizing a Lan-DeMets alpha spending function with an O'Brien-Fleming boundary). An interim OS analysis will be done at the time of the final PFS analysis. It is expected that 149 OS events would have occurred at the time of final PFS analysis.

An interim analysis will be performed after 128 PFS events have been observed. The interim analysis will look into the study's futility using PFS as the efficacy evaluation endpoint. This will utilize a Lan-DeMets error spending-type function with an O'Brien-Fleming stopping boundary with an estimated two-sided beta (Type II error) of 1.2 % spent during this interim look. The interim analysis will be performed by an independent statistician. The independent statistician will evaluate and interpret the results of the interim analysis and will provide corresponding recommendation whether to stop the study for futility or for the study to continue until end of study condition has been met.

Two populations will be defined for the efficacy analysis: Intent-to-treat (ITT; defined as all subjects who were randomized into the study) and per protocol (PP; defined as all subjects in the ITT population who did not have major protocol deviations, have received at least two cycles (8 weeks) of protocol treatment, and met all eligibility criteria). Primary efficacy analysis will be based on ITT where subjects will be analyzed as randomized.

The safety population (SAF) will include all subjects who received at least one dose of either study drug. Subjects will be analyzed as treated.

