4.4 Analysis Populations

- The intent-to-treat (ITT) population will consist of all randomized subjects; this population will be used for efficacy analysis, including primary endpoints. Subjects will be analyzed as randomized.
- The per-protocol (PP) population is defined as all randomized subjects who received at least two cycles (8 weeks) of protocol treatment, had no major protocol deviations that will confound the effects of treatment, and met all eligibility criteria. The PP population will be used as a sensitivity analysis for the assessment of the primary efficacy endpoint, and subjects will be analyzed as treated.
- The safety (SAF) population will include all subjects who received at least one dose of either study drug. Subjects will be analyzed as treated.

The efficacy summaries and analyses will be based on the ITT population. In the event that a subject is allocated the incorrect study treatment as per the study randomization list, subjects will be summarized and analyzed 'as randomized' (i.e. by randomized treatment arm). In the event that a subject is stratified incorrectly, 'randomized stratum' will be used rather than 'actual stratum'.

The safety summaries and analyses will be based on the SAF population. In the event that a subject is allocated the incorrect study treatment as per the study randomization list, subjects will be summarized and analyzed 'as treated' (i.e. by allocated treatment arm).

A by-subject listing of analysis population details will be provided. This listing will be presented by treatment arm and will include: center, subject identifier, inclusion/exclusion flag for each population, and reason for exclusion from each population.

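### Protocol 14.3.4 drops randomized subjects without baseline imaging from the PFS analyses, contrary to its own ITT primary population and to the SAP

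*Protocol*

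**What the plan says.** Protocol 14.3.1 defines the population: "The intent-to-treat (ITT) population will consist of all randomized subjects; this population will be used for efficacy analysis, including primary endpoint". The Synopsis agrees: "Primary efficacy analysis will be based on ITT where subjects will be analyzed as randomized". Protocol 14.3.4 opens by saying that the primary and secondary efficacy "analyses will be carried out using the ITT population".

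Under Handling of Missing Data in the same section, the lead-in is mild ("the following steps will be considered in case of missing data"), but item (a) is not: "Subjects with missing imaging at baseline will be considered non-evaluable for PFS estimation and will be excluded from the PFS analyses". It makes no exception for death. Item (b) deals with subjects who have no tumor assessment after randomization. It keeps them, censored at randomization, unless they died before the second scheduled tumor assessment. Further details and other cases are left to the SAP.

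The protocol's PFS definition takes radiological progression "or death due to any reasons whichever comes first".

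SAP 4.4 has: "The intent-to-treat (ITT) population will consist of all randomized subjects; this population will be used for efficacy analysis, including primary endpoints". SAP 3.2.1 also counts death from any reason, and none of its PFS censoring rules removes a subject for missing baseline imaging. SAP 4.10, which lists changes to the planned analysis, does not mention item (a).

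**The concern.** The protocol cannot both analyze all randomized subjects and leave some of them out. Radiological progression is hard to judge without a baseline scan, but a death needs no scan. Excluding the subject therefore removes an event that the endpoint definition counts.

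The protocol also treats two kinds of missing scan in opposite ways without giving a reason. A missing follow-up scan leads to censoring with early deaths protected. A missing baseline scan leads to removal.

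If item (a) were applied, the primary analysis would become a modified ITT analysis. If the SAP were followed, it would not. A confirmatory trial should have one primary analysis set, fixed in advance. Here it depends on which document is taken to govern. Item (a) also does not say whether missing means not done, not submitted or not readable.

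**Working it through.** **Setting the rules side by side.** Take a randomized subject with no baseline image, no later scan, no new anti-tumor treatment, and death at week 10.

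- Protocol 14.3.4 item (a): excluded.
- Protocol 14.3.4 item (b) and the protocol's PFS definition: event at death.
- SAP 3.2.1 PFS definition: event at death.
- SAP 3.2.1 first PFS censoring rule, read literally (no tumor assessment after randomization, no exception for death): censored at randomization.

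One subject has three possible outcomes in the primary analysis. The text alone establishes the conflict. The arithmetic below only sizes it.

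**The plan's own figure.** Inputs from Protocol 14.2: medians 4 and 6 months, 1:1 allocation, two-sided 5%, 90% power. With exponential PFS the hazard ratio is 4/6 = 0.667. Schoenfeld's formula gives d = 4 × (1.960 + 1.282)² / (ln 1.5)² = 256, against 255 in the plan. Power = Φ(√d / 2 × ln 1.5 − 1.960), which is 89.9% at 255 events. The plan reproduces. At the 242 events targeted for the 04 October 2018 cut-off (Protocol 5.3, SAP 4.10), power is 88.4%.

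**Share excluded.** The documents give none. I assume 0% to 5% of 322, that is 0 to 16 subjects, with average event rates.

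**Deaths that a corrected rule could recover.** Item (b) protects deaths before the second scheduled assessment. With scans every 8 weeks I take this as the second post-baseline scan, at about 16 weeks, or 16 × 7 / 30.44 = 3.68 months. With exponential OS and the plan's medians of 12 and 16 months:

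- sorafenib: 1 − exp(−ln 2 × 3.68 / 12) = 19%
- tivozanib: 1 − exp(−ln 2 × 3.68 / 16) = 15%
- average: about 17%

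So 0 subjects give 0 deaths, 3 subjects (1%) give about 0.5, and 16 subjects (5%) give about 2.7. These are upper figures, since any death after new anti-tumor treatment would be censored under SAP 3.2.1.

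**Effect on power, from 242 events.**

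| Share excluded | Events left under item (a) | Power | Events with early deaths restored | Power | Gain |
|---|---|---|---|---|---|
| 0% | 242 | 88.4% | 242 | 88.4% | 0 |
| 1% | 239.6 | 88.1% | 240.1 | 88.1% | under 0.1 point |
| 5% | 229.9 | 86.7% | 232.6 | 87.1% | about 0.4 points |

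**If the discarded deaths all fell in one arm.** Each would move the log-rank Z by roughly 0.5 / √(255/4) = 0.06, so three would move it by about 0.19. This bounds what is possible. Nothing in the documents shows that it would happen.

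**The case against.** The strongest reply is that the case should hardly arise. Baseline imaging is a screening procedure (Protocol 7.1), measurable disease is an inclusion criterion (6.1), randomization follows only after all eligibility criteria are met (5.4.2), and an independent radiologist verifies measurable disease at screening (14.3.8). The lead-in to item (a) is soft, the protocol leaves further details to the SAP, and an analysis run by the SAP excludes nobody.

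Most of this stands, and it rules out three stronger readings.

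- A reader might infer that the exclusion biases the comparison because receipt of images by the central reader is settled after open-label assignment. The documents do not tie item (a) to central receipt. On their text, a missing baseline scan is mainly a failure before randomization, and exclusion on a pre-assignment characteristic does not by itself unbalance the arms. Because missing is undefined, imbalance cannot be ruled out either.
- A reader might charge item (a) with the whole fall from 88.4% to 86.7% at a 5% share. Most of those events are progressions, which no rule can recover without a baseline.
- A reader might count every death by the cut-off. At the plan's OS medians, with uniform 15-month accrual and 28 months to cut-off, about 63% of subjects have died, or about 10 of 16. Many of those deaths would follow progression or new treatment and are not recoverable PFS events.

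The reply does not remove the conflict. Leaving further details and other cases to the SAP is not permission to drop a stated rule silently, and SAP 4.10 records no such change. The SAP's first censoring rule also loses the early deaths that item (b) protects.

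**Conclusion.** The point holds as a defect in the definition of the primary analysis set. Item (a) contradicts the protocol's all-randomized primary analysis, discards deaths that are events by definition, and differs from the SAP without a recorded change.

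Its numerical size is small: about 0 to 3 recoverable deaths and at most about 0.4 points of power. That rests on an assumed 0% to 5% share, exponential survival at the plan's medians, and a limit of about 16 weeks. The true number affected may be zero. It would be wrong to say that the primary analysis will be a modified ITT analysis, since that follows only if item (a) is applied over the SAP. It would also be wrong to say that the arms will be unbalanced, because the documents do not show it.

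The case for correction rests on the integrity and uniqueness of the analysis set and does not depend on the count.

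**What to change.** 1. Delete item (a) from Protocol 14.3.4. State there and in SAP 3.2.1 that all randomized subjects are in the primary PFS analysis.
2. Treat a subject with no usable baseline image by the rule in item (b): death before the second scheduled tumor assessment, with no earlier new anti-tumor treatment, is an event; otherwise censor at randomization. Define usable.
3. Add this death exception to the first PFS censoring rule in SAP 3.2.1. Align the sentence in the protocol's PFS definition that protects any known death, with no time limit, for subjects without a post-randomization assessment.
4. Record the change in SAP 4.10.
5. If wanted, keep the exclusion as a labelled sensitivity analysis.

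The time limit matters. Counting a death at any time while censoring survivors at randomization would put a subject in the risk set only if he or she dies: a death at month 20 would count, while a survivor at month 20 would contribute no follow-up. The limit in item (b) restrains this, though it does not remove it fully.

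The cost is a few sentences across the two documents and no new data.

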4.2 Secondary Objectives

The secondary objectives of this study are as follows:

- To compare the OS of subjects randomized to treatment with tivozanib or sorafenib
- To compare ORR and duration of response (DoR) of subjects randomized to treatment with tivozanib or sorafenib
- To compare the safety and tolerability of tivozanib and sorafenib.

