4.7.1.4 Multiple Comparisons/Multiplicity

There will be no adjustment for multiplicity. PFS with one treatment contrast (tivozanib vs. sorafenib) is the only primary analysis defined for this study. The secondary analyses are simply intended to provide supportive evidence relating to the primary analysis, therefore, all efficacy endpoints will be assessed without adjustment for multiple comparisons.

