4.7.3 Secondary Efficacy Variables

Overall Survival

The first secondary analysis will compare OS between the two treatment arms by using a stratified log-rank test and the stratification factors included in the primary analysis. The hazard ratio for treatment will be estimated using the stratified Cox proportional hazards regression model.

Summaries showing the 1- and 2-year survival probabilities and corresponding 95% CIs will be provided along with graphical displays (similar to PFS).

Objective Response Rate

The number and proportion of subjects achieving confirmed OR (i.e. confirmed CR or confirmed PR) will be summarized and presented by treatment arm and cycle for the ITT population using a Cochran-Mantel-Haenszel (CMH) test (α =0.05) with the same stratification factors used for the PFS analysis. The odds ratio and associated 95% CI will be calculated. If the expected number in at least one cell is too small (<5), then Fisher's exact test will be used.

In addition, the BOR for each subject will be summarized (number and percentage of subjects in each category).

Duration of Response

Summaries and graphical displays for DoR will be similar to those of OS. This analysis, however, will only apply to subjects that have achieved confirmed OR.

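### The Protocol gives duration of response the PFS log-rank method in responders only, and the SAP does not withdraw it; DoR should be stated as descriptive, with no between-arm test

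*Protocol*

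**What the plan says.** **Objective.** Protocol 4.2 lists as a secondary objective: "To compare ORR and duration of response (DoR) of subjects randomized to treatment with tivozanib or sorafenib". SAP 2.2 repeats it.

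**Method.** Protocol 14.3.4, under the secondary endpoints, says: "Duration of response (DoR) will be analyzed using the same method as for the progression-free survival". For PFS the same section says: "The primary analysis will be carried out by using a stratified Log-Rank test", with three IMDC risk categories and three prior-therapy categories as factors, plus Kaplan-Meier estimates and a median with 95% CI.

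**Analysis set.** The endpoint definitions in Protocol 14.3.4 say: "DoR will only be calculated for the subgroup of subjects with an objective tumor response (PR or CR"). The same section opens with: "The primary efficacy endpoint (PFS) and secondary efficacy endpoints (OS, ORR, and DoR) analyses will be carried out using the ITT population". Both cannot hold literally for DoR.

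**SAP.** Section 4.7.3 names a stratified log-rank test and a Cox hazard ratio for OS, and a CMH test with an odds ratio for response rate. For DoR it says only: "Summaries and graphical displays for DoR will be similar to those of OS", and adds: "This analysis, however, will only apply to subjects that have achieved confirmed OR". SAP 4.10, which lists changes to the planned analysis, does not mention dropping a DoR comparison.

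**The concern.** Response is an outcome of treatment. If tivozanib turns more subjects into responders, its responder group includes subjects who would not have responded on sorafenib and who have no counterpart in the other arm. If their responses are shorter, they pull down tivozanib's DoR, even when every subject who would respond on either drug does at least as well on tivozanib. A log-rank p-value or hazard ratio in responders then does not answer the question in Protocol 4.2, which is about subjects as randomized. The error can go the other way if response rates or durations are reversed.

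Unequal response rates are plausible on the Protocol's own evidence. Section 3.6.2 reports a significantly higher response rate for tivozanib than sorafenib in TIVO-1 (a different, mostly untreated population). The sorafenib label in Appendix E reports confirmed partial responses in 7 sorafenib subjects (2%) in RCC Study 1.

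At stake is a published DoR comparison that could mislead about a named secondary objective. The primary result is not at stake.

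**Working it through.** **1. The plan's own figures.** Neither document gives a sample size, power, expected response rate or expected duration for DoR. The nearest stated figure is for PFS: 255 events for 90% power, two-sided 5%, medians 4 and 6 months. Schoenfeld: 4 × (1.960 + 1.282)² / (ln(4/6))² = 42.03 / 0.1644 = 255.6, so 256 against 255 stated. This confirms the PFS design and says nothing about DoR.

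**2. Assumptions for DoR (none from the documents except 161 per arm).**
- Response rates 8% (sorafenib) and 18% (tivozanib), giving 161 × 0.08 = 12.9 and 161 × 0.18 = 29.0 responders.
- Every subject who responds on sorafenib would also respond on tivozanib, with the same DoR distribution on either drug: exponential, median 12 months.
- The extra tivozanib-only responders (10 of every 18, or 56% of that group) have exponential DoR with median m.
- Censoring uniform from 10 to 24 months.

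By construction, no subject has a shorter response on tivozanib.

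**3. Median in tivozanib responders.** Solve (8/18) × 2^(−t/12) + (10/18) × 2^(−t/m) = 0.5.
- m = 6: with x = 2^(−t/12), 0.556x² + 0.444x − 0.5 = 0 gives x = 0.630 and t = 8.0 months.
- m = 4: 0.556x³ + 0.444x − 0.5 = 0 gives x = 0.699 and t = 6.2 months.

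The sorafenib median is 12 months in both cases.

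**4. Simulated log-rank in responders** (4,000 runs, unstratified, HR = exp((O − E)/V), tivozanib over sorafenib):

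| m (months) | Tivozanib median | HR | Runs pointing against tivozanib | Nominally significant against it (2.5% expected) |
|---|---|---|---|---|
| 12 | 12.0 | 0.96 | 50% | 2% |
| 8 | 9.5 | 1.21 | 70% | 6% |
| 6 | 8.0 | 1.40 | 83% | 13% |
| 4 | 6.2 | 1.65 | 91% | 26% |

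**5. Sensitivity.**
- With response rates of 5/15, 10/20, 10/30 and 20/25% and m from 4 to 8 months, the HR ran from 1.08 to 1.77.
- Over all five pairs with m = 12, it was 0.90 to 0.98, with 48 to 51% of runs against tivozanib, so there was no reversal.
- A variant had shared responders lasting 10% longer on tivozanib and censoring uniform from 6 to 21 months. At 8% vs 18% it gave HRs of 1.59 to 1.68 (m = 4), 1.36 to 1.38 (m = 6) and 1.08 to 1.15 (m = 9) across repeat runs.

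**6. The nine strata.** In that variant, with about 40 to 48 responders and an assumed mix of 20/60/20 by 45/27/28, about 5.5 to 6.3 of the 9 strata had responders in both arms. The stratified test kept about 68 to 75% of the unstratified information. This costs precision; it does not set the direction of the error.

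**7. All randomized subjects, same assumptions.** Mean months in response over 18 months from response onset, with non-responders as zero, is rate × (median/ln 2) × (1 − 2^(−18/median)), summed over responder types.
- Sorafenib: 0.08 × 17.31 × 0.646 = 0.90.
- Tivozanib, m = 6: 0.90 + 0.10 × 8.66 × 0.875 = 0.90 + 0.76 = about 1.65.

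This favours tivozanib, while the responder-only HR of 1.40 points against it.

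**The case against.** **The SAP may already intend description only.** SAP 4.7.3 names tests for OS and response rate and none for DoR, and within the OS text the summaries and plots form a separate paragraph from the test. The natural reading is Kaplan-Meier description in confirmed responders. This stands. A reader might infer that a nine-stratum log-rank test of DoR is settled; the documents do not support that. What they contain is a Protocol sentence and a comparative objective that point to a test, and an SAP section that neither names one nor rules it out.

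**DoR is only supportive.** SAP 4.7.1.4 says: "The secondary analyses are simply intended to provide supportive evidence relating to the primary analysis". DoR has no power calculation or decision rule. This also stands and limits the consequence.

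**The size is assumed.** The distortion needs unequal response rates and shorter responses in the extra responders. A stratified run of the variant was nominally significant against tivozanib in 17 to 19% (m = 4), 9% (m = 6) and 3 to 4% (m = 9) of trials at the two ten-point response-rate gaps, and in 7%, 6% and 3% at 10% vs 15%. A reader might infer that the planned comparison will be biased against tivozanib; it can be, but nothing in the documents shows that it will.

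**An all-randomized measure is a different endpoint.** It mixes response rate with duration: in step 7 the ratio 1.65/0.90 = 1.8 largely restates the response-rate ratio of 18/8 = 2.25. That is fair, and it is why such a measure should be optional.

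**Conclusion.** The concern holds as a gap between Protocol and SAP that leaves open a non-randomized between-arm test of DoR. If that test is run and response rates differ, its p-value and hazard ratio cannot be read as a drug effect on duration. At assumed response rates of 8% and 18%, and a median of 4 to 6 months in the extra responders, the hazard ratio is about 1.4 to 1.7 in the wrong direction. The selection principle is secure; the size is illustrative, because it depends on assumed response rates, nested responders, exponential durations and censoring. The correction is worth making because it is nearly free and removes an inference that randomization does not protect.

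**What to change.** In Protocol 14.3.4, replace the sentence that gives DoR the PFS method, and amend SAP 4.7.3 to match, with wording such as: DoR in confirmed responders is summarized descriptively by arm (Kaplan-Meier median with 95% CI, and plots), with no between-arm test or hazard ratio; the randomized comparison of response is the ITT response-rate analysis. Remove DoR from the sentence in Protocol 14.3.4 that assigns it to the ITT population.

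Optionally, add one supportive analysis: mean time in confirmed response in all randomized subjects, with non-responders counted as zero, measured from randomization to a fixed, prespecified horizon. A censoring-adjusted estimator is the area under the Kaplan-Meier curve for PFS minus the area under the curve for time to first response, progression or death, both up to that horizon. It should be labelled as combining response rate and duration.

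The cost is a wording change in two documents and, if the option is taken, one table from data already collected. The downside is that no DoR p-value in responders can be quoted.
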